6.5. Patient Disposition

Patient flow will be summarized from entered to randomized to completion, and analysis population will be listed and summarized by treatment group.

Patient disposition from study will be listed and summarized with reasons for disposition for the ITT population and the post-treatment follow-up population, respectively.

Patient disposition from study treatment will be listed and summarized for the ITT population for the Blinded Treatment Periods with reasons for disposition, which will be compared between treatment groups using Fisher's exact test.

Time to study treatment discontinuation due to any reason (in weeks) will be summarized by treatment group and graphically presented using Kaplan-Meier Product-Limit method. The log-rank test will be used to compare time to study treatment discontinuation between treatment groups. Time to study treatment discontinuation will be calculated as:

$$\frac{\text{Date of study treatment discontinuation} - \text{Date of first dose} + 1}{7}$$

If the date of first dose is missing, the date of randomization will be used. Patients completing the study treatment will be censored at the date of completion (that is, the date of the last visit in the Blinded Treatment Periods). Patients without a date of completion for the Blinded Treatment Periods will be censored at the latest non-missing date out of the following dates: date of last dose and date of last attended visit in the Blinded Treatment Periods.

6.6. Protocol Deviations

Protocol deviations will be identified throughout the study by monitors and through programmed criteria. Important protocol deviations are defined as those deviations from the protocol likely to have a significant impact on the completeness, accuracy, and/or reliability of the study data or that may significantly affect a subject's rights, safety, or well-being.

The categories and subcategories of important protocol deviations, the source of identification for the deviation, and the statistical programming guidance for the clinical study report (CSR) are included in RHCR Trial Issue Management Plan document.

A by-patient listing of important protocol deviations will be provided. The number and percentage of patients having important protocol deviation(s) will be summarized within category and subcategory of deviations by treatment group for ITT population for the Blinded Treatment Periods.

6.7. Patient Characteristics

6.7.1. Demographics and Baseline Characteristics

Patient demographic variables and baseline characteristics are listed in [Table RHCR.6.3](#) will be summarized for ITT population with the baseline values defined for the Blinded Treatment Periods.

The comparisons between treatment groups will be conducted using an ANOVA model with treatment group as a factor for continuous data, and using Fisher's exact test for categorical data. In the case where Fisher's exact test is too computational intensive, Monte Carlo estimate will be used instead.

By-patient listings of demographic and baseline characteristics, respectively, for the ITT population will be provided.

Table RHCR.6.3. Patient Characteristics and Variables for Subgroup Analysis

Variable ^a	Quantitative Summary	Categorical Summary	Subgroup Analysis ^b
Demographic Characteristics			
Age ^c	Yes	<65 years, ≥65 years to <75 years, ≥75 years	X
		<40 years, ≥40 years	X
Sex	No	Male, Female	X
Age within sex	No	Male <40 years, Male ≥40 years, Female <40 years, Female ≥40 years	
Ethnicity	No	Hispanic/Latino, Non-Hispanic/Non-Latino, Not Applicable	X
Race	No	American Indian/Alaska Native, Asian, Black/African American, Native Hawaiian or other Pacific Islander, White, or Multiple	X
Country	No	United States (including Puerto Rico), Canada	
Height (cm)	Yes	None	
Weight (kg)	Yes	<60 kg, ≥60 kg	
		<80 kg, ≥80 to <100kg, ≥100 kg	
		<90 kg, ≥90 kg	
		<100 kg, ≥100 kg	X
BMI ^d	Yes	Underweight (<18.5 kg/m ²), Normal (≥18.5 and <25 kg/m ²), Overweight (≥25 and <30 kg/m ²), Obese (≥30 and <40 kg/m ²), Extreme obese (≥40 kg/m ²)	X
Prior Psoriasis Therapy			
Prior systemic therapy ^{e,f}	No	Never used, Non-biologic only, Biologic only, Biologic and non-biologic	X
Prior non-biologic systemic therapy ^f	No	Never used, Ever used	X
		0, 1, 2, ≥3	X
Prior non-biologic systemic therapy: inadequate response, loss of response, intolerance or contraindication	No	<3, ≥3	X
Prior biologic therapy ^e	No	Never used, Ever used	X
		0, 1, 2, ≥3	X
Prior biologic therapy class ^e	No	IL-12/23 only, IL-17 only, TNF only, Other only, Multiple	X
Prior anti-TNF alpha ^g	No	Never used, Ever used	X
Prior IL-17 (except ixekizumab) therapy ^h	No	Never used, Ever used	X
Previous topical therapy	No	Never used, Topical prescription therapy only, Topical non-prescription therapy only, Topical prescription and non-prescription therapy	
Previous phototherapy (UVB or PUVA)	No	Never used, PUVA only, UVB only, PUVA and UVB	X
Prior biologic failure ⁱ within prior biologic exposures	No	Not exposed, Exposed but not failed, Exposed and failed	X
Prior systemic failure ⁱ	No	Failed, Not failed	X

Patient Characteristics and Variables for Subgroup Analysis

Variable ^a	Quantitative Summary	Categorical Summary	Subgroup Analysis ^b
Psoriasis Duration and Age at Diagnosis			
Duration of psoriasis diagnosis (years) ^j	Yes	<5 years, 5 to <10 years, 10 to <20 years, ≥20 years	
Age at psoriasis diagnosis (years) ^k	Yes	<25, ≥25	
		<40, ≥40	
Baseline Disease Severity			
Baseline PASI	Yes	<20, ≥20	X
		<15, ≥15	
Baseline sPGA	No	3, 4, 5	X
Baseline BSA (%)	Yes	<20%, ≥20%	X
Baseline PGA-F	No	0, 1, 2, 3, 4	
		< 3, ≥3	X
Baseline Itch NRS	Yes	<4, ≥4	
		=0, >0	
Baseline DLQI	Yes	<5, ≥5	
		<11, ≥11	
Baseline Skin Pain VAS	Yes	=0, >0	
Baseline PatGA	No	0, 1, 2, 3, 4, 5	
Psoriatic arthritis at baseline	No	Yes, No	X
Baseline patient's global assessment of disease activity VAS for patients with baseline psoriatic arthritis	Yes	None	
Baseline patient's assessment of pain VAS for patients with baseline psoriatic arthritis	Yes	None	
Baseline physician's global assessment of disease activity VAS for patients with baseline psoriatic arthritis	Yes	None	

Abbreviations: BMI = body mass index; BSA = body surface area; DLQI = Dermatology Life Quality Index; eCRF = electronic case report form; IL-17 = interleukin-17; NRS = Numeric Rating Scale; PASI = Psoriasis Area and Severity Index; PGA-F = Physician's Global Assessment of Fingernail Psoriasis; PUVA = psoralen ultraviolet A; sPGA = static Physician Global Assessment; TNF = tumor necrosis factor; UVB = ultraviolet B; VAS = visual analog scale.

^a Refer to Sections 6.10 and 6.11 for variable abbreviation.

^b Subgroup analysis will be used for efficacy endpoints only. See Section 6.16.1 for more details.

^c Age (in years) will be calculated as length of the time interval from the imputed date of birth (July 1st in the year of birth collected in the eCRF) to the date that the patient was randomized.

^d BMI will be calculated as: $BMI (kg / m^2) = Weight (kg) / (Height (m))^2$.

^e Biologic therapies (biologic therapy class) include: efalizumab (other), ustekinumab (IL-12/23), infliximab (TNF), etanercept (TNF), alefacept (other), adalimumab (TNF), golimumab (TNF), certolizumab pegol (TNF), secukinumab (IL-17), brodalumab (IL-17), and other biologic agent (other).

^f Non-biologics systemic therapies include: cyclosporine, methotrexate, corticosteroids, acitretin, fumaric acid derivatives, apremilast, and other systemic agent.

^g Anti-TNF alpha biologics include: infliximab, etanercept, adalimumab, golimumab, and certolizumab pegol.

^h Anti-IL-17 (except ixekizumab) biologics include: secukinumab, brodalumab.

ⁱ Reasons for discontinuation are: loss of response; or inadequate response.

- ^j Time since psoriasis diagnosis (years) = $(\text{date of first injection} - \text{date of psoriasis diagnosis} + 1) / 365.25$.
If the date of first dose is missing, the date of randomization will be used. Patients who have a completely missing date of diagnosis will have a missing value for the time since diagnosis, otherwise, “January” and “01” will be imputed for the missing month and day, respectively, in cases where these 2 date components are missing.
- ^k Age at diagnosis in years will be calculated as the time interval from the imputed date of birth (July 1st in the year of birth collected in the eCRF) to the date of psoriasis diagnosis.

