## 5.2. Number of Participants

Approximately 1300 participants will be screened to achieve 960 randomized participants (480 randomized participants per treatment group). Based on experience from the previous UNCOVER-1, -2, -3, and IXORA-S trials, a 5% dropout rate is anticipated.

Patients with previous biologic use can be included in the study provided all inclusion/exclusion criteria, including the washout period(s), as specified in Sections 6.1 and 6.2 of this protocol are respected. Patients with previous exposure to another IL-17 antagonist(s) will be limited to approximately 15% of the total patient population.

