## 6.2. Exclusion Criteria

Patients will be excluded from study enrollment if they meet **any** of the following criteria:

- [9] Have predominant pattern of pustular, erythrodermic, and/or guttate forms of psoriasis.
- [10] Have a history of drug-induced psoriasis.
- [11] Had a clinically significant flare of psoriasis during the 12 weeks before baseline (Week 0, Visit 2).

Medications/Therapies

- [12] Use of tanning booths for at least 4 weeks before baseline (Week 0, Visit 2) and during the study, per investigator assessment.
- [13] Concurrent or recent use of any biologic agent within the following periods prior to baseline (Week 0, Visit 2): etanercept <28 days; infliximab, adalimumab, certolizumab pegol, or alefacept <60 days; golimumab <90 days; rituximab <12 months; secukinumab <5 months; or any other biologic agent (e.g., ustekinumab) <5 half-lives.
- [14] Have prior use of IL-23p19 antagonists (e.g., guselkumab, tildrakizumab, risankizumab), or have any condition or contraindication as addressed in the local labeling for guselkumab that would preclude the patient from participating in this protocol.
- [15] Have previously completed or withdrawn from this study, participated in any other study with ixekizumab or guselkumab, have participated in any study investigating IL-23p19 antagonists, or have received treatment with ixekizumab.
- [16] Have previously failed to respond to an IL-17 antagonist, per investigator assessment.

Vaccinations

- [17] Have had a live vaccination within 12 weeks of baseline (Week 0, Visit 2), or intend to have a live vaccination during the course of the study or within 15 weeks of completing treatment in this study, or have participated in a vaccine clinical study within 12 weeks of baseline. Investigators should review the vaccination status of their patients and follow the local guidelines for adult vaccination with nonlive vaccines intended to prevent infectious disease before therapy.

(Note: killed/inactive or subunit vaccines are expected to be safe; however, their efficacy with concomitant ixekizumab and guselkumab treatment is unknown).

- [18] Have had a vaccination with Bacillus Calmette-Guérin (BCG) within 12 months of baseline (Week 0, Visit 2) or intend to have vaccination with BCG during the course of the study or within 5 half-life of completing treatment in this study.

Medical Status and Medical History

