**Amendment Summary for Protocol I1F-MC-RHCR Amendment (b)**

Section # and Name	Description of Change	Brief Rationale
5.1 Overall Design	Added the following clarification to “the other appropriate means” of patient blinding by the Unblinded Site Personnel: “physical barrier means communicated to the sponsor for final approval.”	Improve clarity
5.2 Number of Participants	Rephrased 1 st sentence of the 2 nd paragraph and replaced “treatment with” with “exposure to” in the last sentence of the 2 nd paragraph.	Improve clarity
6.2 Exclusion Criteria	Exclusion criteria # [15] Removed the restriction of participation in any study investigating other IL-17 antagonists.	Based on recent protocol review and feedback received, a decision was made to be consistent regarding the current or recent use of other IL-17 antagonists. This amendment is to be consistent with the eligible population despite of the source of the exposure. Prior exposure to other IL-17 antagonist in clinical trial settings will be allowed as long as all other inclusion/exclusion criteria are respected; especially > 5 half-lives washout period before baseline visit (Week 0, Visit 2). As specified in Section 5.2 of the protocol, the patient population with previous exposure to another IL-17 antagonist(s) will be limited to approximately 15% of the total patient population.

Section # and Name	Description of Change	Brief Rationale
6.2 Exclusion Criteria	
Exclusion criteria # [22]                      Added the following clarifications:                      “except for basal cell carcinoma, squamous cell carcinoma, skin Bowen’s disease or actinic keratosis that have been treated with no evidence of recurrence in the past 12 weeks or carcinoma in situ of the cervix or non-invasive malignant colon polyps that have been removed.”
	
This addition is to clarify that subjects with the types of non-invasive malignancies and Non-Melanoma Skin Cancers (NMSC), as described in the clarification, can be included in this study, if they have been successfully treated with no evidence of recurrence. This is similar to other biologicals psoriasis studies and aligned with both products labels. In Lilly’s opinion, including such patients in this short study (24 weeks of active treatment periods) will not pose an increased risk of such events since similar populations have previously participated in other biological psoriasis studies.

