6.9.1. Previous Therapy

Previous therapy is defined as the therapy that starts and ends prior to the date of first dose of study treatment in the Induction Dosing Period. If therapy start and/or end dates are missing or partial, the dates will be compared as far as possible with the date of first dose of study treatment in the Induction Dosing Period. If there is clear evidence to suggest that the therapy stopped

prior to the first dose of study treatment in the Induction Dosing Period, the therapy will be assumed to be previous only.

The following summaries will be provided for the ITT population:

- Previous therapy (captured in the *Prior Therapy: Psoriasis* eCRF page and *Concomitant Therapy* eCRF page) by WHO ATC Level 4 and WHO preferred term.
- Previous psoriasis therapy captured in the *Prior Therapy: Psoriasis* eCRF page to be summarized according to type (topical prescription therapy, topical non-prescription therapy, non-biologic systemic agent, biologic agent, non-biologic non-systemic agent, phototherapy) and therapy. The previous biologic agent will be further classified as tumor necrosis factor alpha (TNF- α) inhibitor (includes infliximab, etanercept, adalimumab, golimumab, certolizumab pegol), interleukin- (IL-) 12/23 inhibitor (includes ustekinumab), IL-17 inhibitor (includes secukinumab and brodalumab), and other (includes efalizumab, alefacept, or other biological agent).
- The number and percentage of patients with each reason for discontinuation of previous psoriasis therapy to be summarized by type and therapy.

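### The SAP defines prior IL-17 therapy by two named drugs and sends unlisted biologics to class 'other', while the protocol defines it by class, so an eligible exposed patient could be counted as unexposed

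*SAP*

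**What the plan says.** Protocol 5.2 sets an enrolment limit by drug class, with no list of products: "Patients with previous exposure to another IL-17 antagonist(s) will be limited to approximately 15% of the total patient population". Table RHCR.7.3 of the protocol repeats the limit. Exclusion criterion [15] in Protocol 6.2 bars earlier participation in studies of ixekizumab, guselkumab or IL-23p19 antagonists, and anyone who may "or have received treatment with ixekizumab". It does not bar earlier studies of other IL-17 antagonists. The rationale given for amendment (b) shows that this is intended: "Prior exposure to other IL-17 antagonist in clinical trial settings will be allowed as long as all other inclusion/exclusion criteria are respected".

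The SAP derives the exposure from named drugs in three places:

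- Table RHCR.6.3, footnote e (biologic class): "secukinumab (IL-17), brodalumab (IL-17), and other biologic agent (other".
- Table RHCR.6.3, footnote h (the variable "Prior IL-17 (except ixekizumab) therapy", coded never or ever used): "Anti-IL-17 (except ixekizumab) biologics include: secukinumab, brodalumab".
- SAP 6.9.1 (summary of previous psoriasis therapy): "IL-17 inhibitor (includes secukinumab and brodalumab), and other (includes efalizumab, alefacept, or other biological agent".

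Both the biologic-class variable and the prior IL-17 variable are marked for subgroup analysis. SAP 6.17.1 tests each subgroup-by-treatment interaction at 0.10, and gives summaries only when any category holds less than 10% of the ITT population.

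**The concern.** The two documents describe the same exposure in different ways. A patient can count as IL-17-exposed for the protocol's limit and as unexposed in the SAP's subgroup variable.

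This subgroup has an obvious clinical reading. Ixekizumab is an IL-17A antagonist and guselkumab acts on IL-23, and prior use of IL-23p19 antagonists is excluded by criterion [14]. Earlier exposure to the class of one study drug but not of the other is therefore a natural question for a reader of the trial. If some exposed patients sit in the unexposed category, the baseline table understates prior IL-17 use and the subgroup contrast is not quite the one its label promises.

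**Working it through.** There is no figure in the plan to reproduce here, because the point concerns a coding rule. The check sets the passages side by side and then gauges the scale.

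**1. Can such a patient enrol?** Yes. Criterion [15] excludes prior ixekizumab but not other IL-17 antagonists. Criterion [13] admits other biologics after the stated washout. Criterion [16] removes only patients who failed to respond to an IL-17 antagonist. Trial exposure is expressly allowed in the amendment (b) rationale.

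**2. How does the SAP code the patient?** The table compares the literal two-drug rule with a rule based on mechanism. I take *Multiple* to mean more than one class; the SAP does not define it.

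| Prior biologics | Class, literal | Class, by mechanism | Prior IL-17, two-drug list | Prior IL-17, by mechanism |
|---|---|---|---|---|
| Unlisted IL-17 agent alone | Other only | IL-17 only | Never used | Ever used |
| Unlisted IL-17 agent and a TNF inhibitor | Multiple | Multiple | Never used | Ever used |
| Unlisted IL-17 agent and secukinumab or brodalumab | Multiple | IL-17 only | Ever used | Ever used |
| Secukinumab or brodalumab alone | IL-17 only | IL-17 only | Ever used | Ever used |

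The prior IL-17 variable goes wrong only in the first two rows, where the patient took no listed IL-17 drug. Ixekizumab creates no error, since prior use is excluded and the variable's label sets it aside.

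**3. Is there a rule that would correct this?** I found none. SAP 6.9 codes medications with the WHO drug dictionary for the therapy summaries, but nothing links that coding to the Table RHCR.6.3 variables or reclassifies other-biologic entries by mechanism.

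**4. How large could it be?** Inputs: planned N = 960 (Protocol 5.2), limit of about 15% (Protocol 5.2), testing threshold of 10% of ITT (SAP 6.17.1). The number of affected patients, m, is not in the documents and is an assumption.

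- Exposed patients at the limit: 0.15 × 960 = 144.
- Testing threshold: 0.10 × 960 = 96.
- With E truly exposed, the *Ever used* count is E − m, and inferential testing is dropped when E − m < 96.
- E = 144, m = 0: 144 of 960 (15.0%).
- E = 144, m = 48: 96 of 960 (10.0%), still tested.
- E = 144, m = 49: 95 of 960 (9.9%), summaries only. The *Never used* group is then 960 − 95 = 865, of whom 49 / 865 = 5.7% are in fact exposed.
- E = 110: testing is lost at m = 15, since 110 − 15 = 95.
- E below 96: no inferential testing, whatever the coding.

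**The case against.** The strongest reply is that footnote h says *include*, which may introduce examples, and the variable itself is named by class. On that reading a programmer could code an unlisted IL-17 agent as *Ever used*. This has some force, and it is why the result is stated as one that could occur. It does not settle the matter. The explicit catch-all in footnote e and in SAP 6.9.1 places unlisted biologics in 'other', and footnotes e and f show that the SAP writes a catch-all where it wants one, while footnote h has none.

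A second reply is that nobody may be affected. The documents name only three IL-17 antagonists (ixekizumab, secukinumab and brodalumab), the SAP's country categories are the United States and Canada, and washout and the exclusion of IL-17 non-responders narrow entry. That stands: the number is unknown and may be zero.

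Three stronger readings are tempting, and the documents do not support them:

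- *Every patient with an unlisted IL-17 agent becomes Never used.* Not so: anyone who also took secukinumab or brodalumab stays *Ever used*.
- *The 15% limit can no longer be checked.* It is an enrolment limit, and nothing ties its monitoring to the Table RHCR.6.3 variable. The preferred-term summary in SAP 6.9.1 could also show an agent by name if it was recorded by name.
- *The interaction test is materially blurred, or its inferential testing will be lost.* No effect on the interaction estimate or its power is shown. Losing the test needs 49 affected patients at the limit, or a lower true exposure, and nothing in the documents points to either.

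**Conclusion.** The mismatch is real and minor. An explicit SAP rule assigns the wrong class to a type of patient whom the protocol deliberately admits, and the two-drug footnote could carry that error into the prior IL-17 subgroup. The conclusion rests on the literal reading of footnotes e and h together and on at least one enrolled patient having taken an unlisted IL-17 agent.

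The effect is confined to baseline and previous-therapy summaries and to the exploratory subgroup analyses by prior IL-17 therapy and by biologic class. The Week 12 primary analysis, the nine-step test sequence and the sample size are untouched. The counts in the working show scale only and are not forecasts.

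**What to change.** In Table RHCR.6.3, footnotes e and h, and in SAP 6.9.1, define the class by mechanism, for example: *IL-17: secukinumab, brodalumab, or any other IL-17 or IL-17 receptor antagonist recorded under other biologic agent.* Add that other-biologic entries are classified by mechanism in a blinded review of the recorded terms. The review should be finished before the Week 12 database lock, when part of the study team is unblinded under Protocol 10.3.7. The SAP variable would then match the protocol's class definition.

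The cost is a change of wording in three places and a short coding review. Timing matters because moving patients between subgroup categories after unblinding would be open to challenge.

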6.8. Historical Illnesses and Preexisting Conditions

Historical illnesses and preexisting conditions will be classified using the latest version of MedDRA.

Historical illness/condition is defined as the condition/event recorded on the *Preexisting Conditions and Medical History* electronic case report form (eCRF) page or on the *Prespecified Medical History* eCRF page with an end date prior to the date of informed consent.

Preexisting condition is defined as the condition/event recorded on the *Preexisting Conditions and Medical History* eCRF page or on the *Prespecified Medical History* eCRF page with a start date prior to the date of informed consent, and no end date (that is, the event is ongoing) or an end date on or after the date of informed consent. Preexisting conditions and AEs occurring prior to first dose will be reported. Notice if a preexisting condition worsens in severity on or after the date of informed consent, it will be recorded as an AE on *Adverse Events* eCRF page from the date of worsening onwards.

The following summaries will be provided for the ITT population:

- The number and percentage of patients with historical illnesses by treatment and overall, by System Organ Class (SOC) and preferred term.
- The number and percentage of patients with preexisting conditions by treatment and overall, by SOC and preferred term.
- The number and percentage of patients with prespecified medical history (hypertension; diabetes mellitus, Type I; diabetes mellitus, Type II insulin dependent; diabetes mellitus, Type II non-insulin dependent; coronary artery disease; stroke; dyslipidemia; psoriatic arthritis; Crohn’s disease; ulcerative colitis), by treatment and overall.

